### **9.3 Potential Benefit**

Study participants may or may not receive any direct benefits from their participation in this study. Administration of lopinavir/ritonavir may improve clinical outcomes among outpatient adults with COVID-19.

### **9.4 Risk in Relation to Anticipated Benefit**

Federal regulations at 45 CFR 46.111 (a)(2) require that “the risks to subjects are reasonable in relation to anticipated benefits, if any, to subjects, and the importance of the knowledge that may reasonably be expected to result.” Based on the preceding assessment of risks and potential benefits, the risks to subjects are reasonable in relation to anticipated benefits. Lopinavir/Ritonavir has been used in clinical practice for decades and previously evaluated for the treatment of patients acutely ill from infection with substantial data to support its safety and potential efficacy.

## **10. HUMAN SUBJECTS PROTECTIONS**

Each study participant must sign and date an informed consent form or complete the consent in accordance with ethics committee guidelines for obtaining consent. Approval of the central institutional review board will be required before any participant is entered into the study.

### **10.1 Selection of Subjects**

Federal regulations at 45 CFR 46(a)(3) require the equitable selection of subjects. We will screen non-hospitalized patients with positive SARS-CoV-2 testing to determine if a patient meets inclusion and exclusion criteria. Data that have been collected as part of the routine clinical care of the patient will be reviewed to determine eligibility. Study exclusion criteria neither unjustly exclude classes of individuals from participation in the research nor unjustly include classes of individuals for participation in the research. Hence, the recruitment of participants conforms to the principle of distributive justice.

### **10.2 Informed Consent**

Federal regulations 45 CFR 46.111(a)(5) require us to seek informed consent from each patient. Study personnel obtaining informed consent are responsible for ensuring that the patient understands the risks and benefits of participating in the study, answering any questions the patient may have throughout the study and sharing any new information in a timely manner that may be relevant to the patient’s

willingness to permit the patient's continued participation in the trial. The study personnel obtaining informed consent will make every effort to minimize coercion. We will inform all patients of the objectives of the study and the potential risks. We will use the informed consent document to explain the risks and benefits of study participation to the patient in simple terms before the patient is entered into the study, and to confirm that the patient is satisfied with his or her understanding of the risks and benefits of participating in the study and desires to participate in the study. The investigator is responsible for ensuring that informed consent is given by each patient. This includes obtaining the appropriate signatures and dates on the informed consent document prior to the performance of any protocol procedures including administration of study agent.

For additional details, see Section 3.6.

### **10.3 Withdrawal of Consent**

Participating patients may withdraw or be withdrawn (by the treating physician or investigator) from the trial at any time without prejudice. Site personnel will include data up to the point of withdrawal in the trial analysis, unless consent to use data is also withdrawn. Site personnel will record consent prior to receipt of study drug, which will constitute a screen-failure. Withdrawal of consent after randomization and administration of one or more doses of study drug will lead to discontinuation of study interventions but site staff will request access to medical records for data related to the trial.

### **10.4 Confidentiality**

Federal regulations at 45 CFR 46 111 (a) (7) requires that when appropriate, there are adequate provisions to protect the privacy of participants and to maintain the confidentiality of data. At no time during the course of this study, its analysis, or its publication will we reveal patient identities in any manner. We will collect the minimum necessary data containing patient or provider identities. All patients will be assigned a unique study ID number for tracking. We will enter all data collected for this study into a secure online database. We will maintain all data in the secure online database until the time of study publication. At the time of publication, we will generate a de-identified version of the database. Further, we will use tools within the secure online database so that only the coordinating center and investigators from the enrolling site will have access to data from participants enrolled at that site.

## **11. ADVERSE EVENTS**

Assuring patient safety is an essential component of this protocol. Lopinavir/ritonavir is approved by the Food and Drug Administration and there is an have been used in clinical practice for decades with a well-established safety profile. Use of lopinavir/ritonavir for the treatment of acute respiratory infection due to COVID-19, however, raises unique safety considerations. This protocol addresses these considerations through:

1. Exclusion criteria designed to prevent enrollment of patients likely to experience adverse events with receipt of lopinavir/ritonavir
2. On-study monitoring of co-interventions (e.g., newly prescribed medications) and patient characteristics (e.g., healthcare utilization, clinically obtained electrocardiogram) to intervene before adverse events occur.
3. Systematic collection of safety outcomes relevant to use of lopinavir/ritonavir in this setting.

#### 4. Structured reporting of adverse events

### 11.1 Adverse Event Definitions

**Adverse Event:** Any untoward medical occurrence associated with the use of a drug or a study procedure, whether or not considered drug related.

**Serious Adverse Event:** A serious adverse event is any adverse event that results in one of the outcomes listed in section 11.3 below.

**Adverse Reaction:** An adverse reaction means any adverse event caused by a study intervention. An adverse reaction is a subset of all suspected adverse events where there is a reason to conclude that the study intervention caused the event.

**Suspected Adverse Reaction:** Any adverse event for which there is a reasonable possibility that the study procedures caused the adverse event. Reasonable possibility means there is evidence to suggest a causal relationship between the study procedures and the adverse event. A suspected adverse reaction implies a lesser degree of certainty about causality than adverse reaction.

**Suspected Unexpected Serious Adverse Reaction (SUSAR):** An adverse reaction that is both unexpected (not consistent with risks outlined in the study protocol or investigator brochure), serious, and meets the definition of a suspected adverse reaction.

### 11.2 Safety Monitoring

Assuring patient safety is an essential component of this protocol. Each participating investigator has primary responsibility for the safety of the individual participants under his or her care. The Investigators will determine daily if any adverse events occur during the period from enrollment through **study day 16** (or 48 hours after completion of the study drug administration) and will determine if such adverse events are reportable. Thereafter, adverse events are not required to be reported to the IRB unless the investigator feels the adverse event was related to study drug or study procedures.

The following adverse events will be considered reportable and thus collected in the adverse event case report forms:

- Serious adverse events
- Non-serious adverse events that are considered by the investigator to be related to study procedures or of uncertain relationship (Appendix C)
- Events leading to permanent discontinuation of study drug.

Study-specific clinical outcomes (Primary, Secondary and Safety Outcomes and Assessments During the Study), including serious outcomes such as organ failures and death, are systematically recorded in the case report forms and are exempt from adverse event reporting unless the investigator deems the event to be related to the administration of study drug or the conduct of study procedures (or of uncertain relationship) as outlined in Appendix C.

After randomization, adverse events must be evaluated by the investigator. If the adverse event is judged to be reportable, as outlined above, then the investigator will report to the VCC their assessment of the

potential relatedness of each adverse event to the study drug or protocol procedure via electronic data entry. Investigators will assess if there is a reasonable possibility that the study procedure caused the event, based on the criteria outlined in Appendix C. Investigators will also consider if the event is unexpected. Unexpected adverse events are events not listed in the study protocol and the investigator brochure for Lopinavir/ritonavir. Investigators will also determine if adverse events are unanticipated given the patient's clinical course, previous medical conditions, and concomitant medications.

If a patient's treatment is discontinued as a result of an adverse event, study site personnel must also report the circumstances and data leading to discontinuation of treatment in the adverse event case report forms.

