## 6.1 Baseline Variable Collection

- Informed Consent Document and documentation of consent process
- Presence or absence of each inclusion and exclusion criterion
- Date and time of enrollment
- Day of symptom onset
- Specimen type, date, and result of SARS-CoV-2 testing conducted clinically.
- Demographics (age, sex, race, ethnicity, height, weight)
- Comorbidities: chronic cardiac disease, chronic pulmonary disease, chronic kidney disease, chronic liver disease, chronic neurological disease, malignant neoplasm, chronic hematologic disease, AIDS/HIV, obesity, diabetes with complications, diabetes without complications, rheumatologic disorder, malnutrition, smoking, other
- Chronic use of medication: ACE inhibitors, angiotensin receptor blockers
- Receipt of azithromycin in the past week
- Presenting signs and symptoms, along with self-reported severity

## 6.2 Daily Assessments between Randomization and Study Day 16, and then at Day 29

- Study drug administration and reason for missed doses.
- Modified COVID Ordinal Outcomes Scale
- Daily signs and symptoms, along with self-reported severity via electronic log and/or telephone interview.
- Day of symptom resolution
- Receipt of open label antivirals: chloroquine, hydroxychloroquine, remdesivir, lopinavir/ritonavir, other
- Receipt of open label immunomodulators between enrollment and hospital discharge: corticosteroids, tocilizumab, sarilumab, interferon  $\beta$ , other
- Receipt of azithromycin
- Study days in hospital (if applicable)
- Study days receiving supplemental oxygen (if applicable)
- Study days receiving non-invasive or invasive mechanical ventilation (if applicable)
- Study days in ICU to Study Day 29
- Study day of death (if applicable)
- Safety Outcomes: seizure, atrial or ventricular arrhythmia, cardiomyopathy, cardiac arrest, aspartate aminotransferase or alanine aminotransferase levels that are greater than twice the local upper limit of normal (or two times higher than known baseline), acute pancreatitis (defined by a clinically obtained lipase level above the local upper limit of normal and abdominal pain or vomiting), stage II or greater acute kidney injury according to KDIGO criteria, receipt of new renal replacement

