#### **9.1.2 Potential risks of receiving lopinavir/ritonavir**

The safety and tolerability of lopinavir/ritonavir has been well characterized through clinical trials and post-marketing experience since first authorization for use in 2001 for the approved HIV indication with over 7 million patient years of exposure. Based on clinical trials and post-marketing experience, the most frequently reported adverse drug reactions among patients receiving lopinavir/ritonavir were gastrointestinal disorders (including diarrhea, nausea, vomiting, and upper and lower abdominal pain), fatigue/asthenia, respiratory tract infection (upper and lower), lipid elevations (hypercholesterolemia and hypertriglyceridemia), musculoskeletal pain (including arthralgia and back pain), and headache (including migraine). Key safety concerns include metabolic abnormalities such as dyslipidemia and insulin resistance, pancreatitis, and hepatotoxicity. In addition, in the HIV population, immune reconstitution inflammatory syndrome (IRIS) manifesting as autoimmune disorders (such as Grave's disease) has been reported.

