### **C.2. Determining Relationship of Adverse Events to Study Drug or Study Procedures**

Investigators will be asked to grade the strength of the relationship of an adverse event to study drug or study procedures as follows:

- Definitely Related: The event follows: a) A reasonable, temporal sequence from a study procedure; and b) Cannot be explained by the known characteristics of the patient’s clinical state

or other therapies; and c) Evaluation of the patient's clinical state indicates to the investigator that the experience is definitely related to study procedures.

- Probably or Possibly Related: The event should be assessed following the same criteria for "Definitely Associated". If in the investigator's opinion at least one or more of the criteria are not present, then "probably" or "possibly" associated should be selected.
- Probably Not Related: The event occurred while the patient was on the study but can reasonably be explained by the known characteristics of the patient's clinical state or other therapies.
- Definitely Not Related: The event is definitely produced by the patient's clinical state or by other modes of therapy administered to the patient.
- Uncertain Relationship: The event does not meet any of the criteria previously outlined.

[figure not shown]

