6.2 Inclusion-Exclusion Criteria and General Study Population

Patients aged ≥ 18 years who have laboratory-confirmed SARS-CoV-2 infection by RT-PCR or other molecular test within the past 6 days, whose symptoms began ≤ 6 days previously, and who currently remain with at least one symptom are eligible to participate. Qualifying symptoms are cough, fever, shortness of breath, chest pain, abdominal pain, nausea/vomiting, diarrhea, body aches, weakness/fatigue.

Detailed exclusion criteria are listed in the protocol. They include known contraindications for lopinavir/ritonavir, clinical conditions increasing the risk of adverse events associated with lopinavir/ritonavir, known pregnancy or breast feeding, known to be a prisoner, inability to comply with study procedures, and inability to provide informed consent or complete daily symptom surveys in English or Spanish during the two-week observational period.

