- Other (Not Including Serious) Adverse Events: A table of anticipated and unanticipated events (not included in the serious adverse event table) that exceed a frequency threshold of 5% within any arm of the clinical study, grouped by organ system, with number and frequency of such events in each arm/group of the clinical study.

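### Non-serious events that do not end treatment reach the adverse event form only through investigator attribution, the drug's commonest reactions are also entry symptoms, and no symptom-specific safety comparison by arm is planned

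*Protocol*

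**What the plan says.** **Collection.** Protocol 11.2 sends three kinds of event to the adverse event form: serious events; "Non-serious adverse events that are considered by the investigator to be related to study procedures or of uncertain relationship (Appendix C"; and "Events leading to permanent discontinuation of study drug". Study outcomes and the assessments made during the study "are exempt from adverse event reporting unless the investigator deems the event to be related to the administration of study drug"; a suspected link to a study procedure, or doubt about the link, also makes such an event reportable.

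**Attribution.** Appendix C.2 includes a grade of Probably Not Related for an event that "can reasonably be explained by the known characteristics of the" patient's clinical state or other therapies.

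**Expected reactions and entry symptoms.** Protocol 9.1.2 names among the most frequent reactions "gastrointestinal disorders (including diarrhea, nausea, vomiting, and upper and lower abdominal pain), fatigue/asthenia". SAP 6.2 states: "Qualifying symptoms are cough, fever, shortness of breath, chest pain, abdominal pain, nausea/vomiting, diarrhea, body aches, weakness/fatigue".

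**Data collected without a stated attribution filter.** Protocol 6.1 records presenting symptoms with self-reported severity. Protocol 6.2 adds "Daily signs and symptoms, along with self-reported severity via electronic log and/or telephone interview", and also self-reported adverse events to Study Day 15.

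**Analysis.** SAP 5.3 defines the safety outcomes as potentially associated adverse events plus an open list of named events. No gastrointestinal symptom and no fatigue item is named. SAP 11 plans tables of mortality, of serious events and, for the rest, "A table of anticipated and unanticipated events (not included in the serious adverse event table) that exceed a frequency threshold of 5" per cent in any arm, with the whole safety population as denominator. SAP 11.1 adds a summary of discontinuation from self-report.

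**The concern.** Describing the safety profile is a secondary objective (SAP 5.1). For this drug the main tolerability question is gastrointestinal, and Protocol 9.1.2 itself warns of frequent diarrhea and its consequences. A participant with COVID-19 who reports diarrhea on Study Day 5 may have it from the drug or from the infection, and a blinded investigator working remotely has little with which to tell them apart.

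If the event is put down to the illness, is not serious and does not end treatment, it never reaches the form. Filtering events in this way gives up part of what randomization provides. Background symptoms should be balanced between arms, so a plain count by arm would estimate the drug's contribution without anyone having to assign a cause. The plan collects the data for such a count but does not schedule it as a safety analysis.

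**Working it through.** No stated figure is in dispute, so the check is mainly a reading of the sections against each other, followed by an illustration on assumed rates.

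**Step 1: overlap.** Diarrhea, nausea, vomiting, abdominal pain and fatigue appear both in Protocol 9.1.2 as common reactions and in Protocol 3.1 and SAP 6.2 as qualifying symptoms.

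**Step 2: what happens to an overlapping, non-serious event.**
- It leads to permanent discontinuation: recorded, whatever the attribution.
- It is graded definitely, probably or possibly related, or uncertain: recorded.
- It is graded Probably Not Related because the illness can explain it: not recorded on the form.

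Appendix C.2 does not settle which of the last two applies. An event that COVID-19 could explain fits Probably Not Related. It also fails one criterion of Definitely Related, and C.2 then directs the rater to probably or possibly. The uncertain grade is kept for events that meet none of the other definitions. The bullet in 11.2 also speaks of study procedures, where the exemption paragraph names the study drug as well; the wording should be reconciled.

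**Step 3: other routes.** The self-reported adverse events in Protocol 6.2 carry no stated filter. Neither document says whether they enter the SAP 11 table.

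**Step 4: other uses of the symptom data.** After baseline the SAP uses symptoms for scale levels 5 to 7, time to symptom resolution and fever-free days. All are efficacy measures, and none separates the symptoms listed in Step 1.

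**Step 5: size, on assumed rates.** Inputs: about 300 per arm (600 planned, 1:1, SAP 6.3 and 7). True rates and the attributed share *s* are not in the documents. I assumed placebo 10–30%, active 20–50%, and *s* from 10% to 100%, equal in both arms.

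Recorded rate = true rate × *s*, so recorded difference = true difference × *s*.

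Power for two proportions, two-sided 0.05: Φ[(d − 1.96·SE0)/SE1], where SE0 uses the mean of the two rates and SE1 the separate rates. For 20% vs 35% with *s* = 1:
- SE0 = √(2 × 0.275 × 0.725/300) = 0.0365
- SE1 = √((0.20 × 0.80 + 0.35 × 0.65)/300) = 0.0359
- (0.15 − 1.96 × 0.0365)/0.0359 = 2.19, so power is 98.6%

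| Share attributed | Recorded rates | Difference (points) | Power |
|---|---|---|---|
| 100% | 20% vs 35% | 15 | 98.6% |
| 50% | 10% vs 17.5% | 7.5 | 76% |
| 25% | 5% vs 8.75% | 3.75 | 44% |
| 10% | 2% vs 3.5% | 1.5 | 20% |

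From 10% vs 20% up to 30% vs 50%, power is 93% to 99.9% with full counting and 36% to 53% at *s* = 25%. The SAP plans no test here; power only expresses how visible the difference would be.

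**Step 6: the 5% threshold.** Five per cent of 300 is 15 participants. A reaction enters the table only if *s* exceeds 5% divided by its true rate in the arm where it is commoner: 50% for a true rate of 10%, 25% for 20%, 17% for 30% and 12.5% for 40%.

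**The case against.** **Attribution is not the only route.** This stands. Permanent discontinuations are recorded whatever the cause. Self-reported adverse events and reasons for missed doses are collected, and SAP 11.1 summarizes discontinuation from self-report. A reader might infer that the whole tolerability result hangs on investigator judgement. The documents do not support that, because they leave open which source feeds the non-serious table.

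**Investigators who cannot tell have recordable grades.** This is fair: possibly related and uncertain are both reportable. No document supports an attributed share as low as 25% or 10%. Probably Not Related is nevertheless available for exactly these events, so some loss is likely, of unknown extent.

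**Attribution may differ by arm.** A reader might infer this from the unmatched placebo. If 15% in each arm truly had diarrhea, and 60% of active-arm events but 20% of placebo events were attributed, the table would show 9% vs 3%. Nothing in the documents shows this. Investigators are blinded, telephone contacts avoid the tablets' appearance, and Protocol 4.3 argues that a participant who looks up the markings could still believe the tablet is a matched placebo. It is possible, not shown.

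**With equal shares the ratio survives.** True: 20% vs 35% and 5% vs 8.75% are both 1 to 1.75. The absolute difference shrinks, and the row may fall below the threshold.

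**Symptoms are already compared by arm.** They are, whatever their cause, in the primary scale and in time to symptom resolution, so drug-induced diarrhea reported as a symptom can count against the active arm. What is missing is a comparison symptom by symptom.

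**Limited reporting is a reasoned choice.** The protocol defends a pragmatic, remote design for an approved drug (6, 9.1.2, 9.2), and the SAP 5.3 list is open. That justifies a short form. It does not argue against tabulating data already held.

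**Conclusion.** The point holds in a limited form. Non-serious events that do not permanently end treatment reach the adverse event form only if judged related or uncertain. The commonest reactions overlap the disease, and one attribution grade lets overlapping events drop out. The non-serious table is therefore likely to understate the absolute difference between arms. If the attributed share is equal in both arms, the recorded difference is that share of the true one; the share is unknown, and every rate used above is an assumption.

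The primary analysis is not affected. This is a cheap improvement to a secondary objective, not a flaw that invalidates the safety plan. How far it bites depends on whether the self-reported adverse events feed the table, which the SAP should state in any case.

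**What to change.** In SAP 5.3 and 11:

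1. Add one by-arm table in the safety population, regardless of attribution. For each of diarrhea, nausea/vomiting, abdominal pain and fatigue, give the proportion of participants whose symptom is new, or at least one severity grade worse than at baseline, on any of Study Days 2 to 15, and the number of such days.
2. Keep the non-serious adverse event table and state its data source, including whether the self-reported adverse events of Protocol 6.2 enter it. If they do not, label it as holding only related, uncertain or discontinuation events.

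**Cost.** SAP wording and one extra table. No new data are needed if the daily survey grades the same symptoms as at baseline. That is an assumption: the form is not in the documents, the only severity grades shown are for fever (SAP 5.3), and SAP 9.1 summarizes baseline symptoms as yes or no. Background COVID-19 symptoms will dilute the contrast but are balanced by randomization. Self-report may be influenced if participants recognise the unmatched tablets, so the new table should stand beside the attributed one and not replace it.
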